APPENDIX 4 WOMEN OF CHILDBEARING POTENTIAL DEFINITIONS AND METHODS OF CONTRACEPTION

DEFINITIONS

Woman of Childbearing Potential (WOCBP)

A woman is considered fertile following menarche and until becoming postmenopausal unless permanently sterile. Permanent sterilization methods include hysterectomy, bilateral salpingectomy, and bilateral oophorectomy.

Women in the following categories are not considered WOCBP:

- Premenarchal
- Premenopausal female with 1 of the following:
 - Documented hysterectomy
 - Documented bilateral salpingectomy
 - Documented bilateral oophorectomy

Note: Documentation can come from the site personnel's review of the participant's medical records, medical examination, or medical history interview.

- Postmenopausal female
 - A postmenopausal state is defined as 12 months of amenorrhea in a woman over age 45 years in the absence of other biological or physiological causes. In addition, females under the age of 55 years must have a serum follicle stimulating hormone (FSH) level > 40 mIU/mL to confirm menopause.

CONTRACEPTION GUIDANCE FOR FEMALE PARTICIPANTS OF CHILDBEARING POTENTIAL

One of the highly effective methods of contraception listed below is required during study duration and until the end of relevant systemic exposure, defined as 5 months after the end of study treatment.*

Highly Effective Contraceptive Methods That Are User Dependent

Failure rate of < 1% per year when used consistently and correctly.^a

- Combined (estrogen- and progestogen-containing) hormonal contraception associated with inhibition of ovulation/or implantation (These methods of contraception cannot be used by WOCBP participants in studies where hormonal contraception is prohibited)^b
 - oral (birth control pills)
 - intravaginal (vaginal birth control suppositories, rings, creams, gels)
 - transdermal

- Progestogen-only hormonal contraception associated with inhibition of ovulation^b
 - oral
 - injectable

Highly Effective Methods That Are User Independent

- Implantable progestogen-only hormonal contraception associated with inhibition of ovulation and/or implantation (This method of contraception cannot be used by WOCBP participants in studies where hormonal contraception is prohibited)^b
- Intrauterine hormone-releasing system (IUS)(This method of contraception cannot be used by WOCBP participants in studies where hormonal contraception is prohibited)^c
- Intrauterine device (IUD)^c
- Bilateral tubal occlusion
- Vasectomized partner

A vasectomized partner is a highly effective contraception method provided that the partner is the sole male sexual partner of the WOCBP and the absence of sperm has been confirmed. If not, an additional highly effective method of contraception should be used.

- Sexual abstinence

Sexual abstinence is considered a highly effective method only if defined as refraining from heterosexual intercourse during the entire period of risk associated with the study drug. The reliability of sexual abstinence needs to be evaluated in relation to the duration of the study and the preferred and usual lifestyle of the participant.

- It is not necessary to use any other method of contraception when complete abstinence is elected.
- WOCBP participants who choose complete abstinence must continue to have pregnancy tests, as specified in [Section 2](#).
- Acceptable alternate methods of highly effective contraception must be discussed in the event that the WOCBP participants chooses to forego complete abstinence

NOTES:

^a Typical use failure rates may differ from those when used consistently and correctly. Use should be consistent with local regulations regarding the use of contraceptive methods for participants participating in clinical studies.

^b Hormonal contraception may be susceptible to interaction with the study drug, which may reduce the efficacy of the contraceptive method. Hormonal contraception is permissible only when there is sufficient evidence that the IMP and other study medications will not alter hormonal exposures such that contraception would be ineffective or result in increased exposures that could be potentially hazardous. In this case, alternative methods of contraception should be utilized.

^c Intrauterine devices and intrauterine hormone releasing systems are acceptable methods of contraception in the absence of definitive drug interaction studies when hormone exposures from intrauterine devices do not alter contraception effectiveness

Unacceptable Methods of Contraception*

- Male or female condom with or without spermicide. Male and female condoms cannot be used simultaneously
- Diaphragm with spermicide
- Cervical cap with spermicide
- Vaginal Sponge with spermicide
- Progestogen-only oral hormonal contraception, where inhibition of ovulation is not the primary mechanism of action
- Periodic abstinence (calendar, symptothermal, post-ovulation methods)
- Withdrawal (coitus interruptus).
- Spermicide only
- Lactation amenorrhea method (LAM)

*** Local laws and regulations may require use of alternative and/or additional contraception methods.**

CONTRACEPTION GUIDANCE FOR MALE PARTICIPANTS WITH PARTNER(S) OF CHILD BEARING POTENTIAL.

- Given that nivolumab is not a genotoxic agent, and that relevant systemic concentrations sufficient to produce a risk of fetal toxicity are not expected in WOCBP partners from exposure to a male participant's seminal fluid, male study participants will not be required to use contraceptive measures and/or a latex or other synthetic condom during sexual activity with a WOCBP partner.

COLLECTION OF PREGNANCY INFORMATION

Guidance for collection of Pregnancy Information and outcome of pregnancy on the Pregnancy Surveillance Form is provided in [Section 9.2.5](#) and the Appendix for Adverse Events and Serious Adverse Events Definitions and procedures for Evaluating, Follow-up and Reporting

APPENDIX 5 MANAGEMENT ALGORITHMS

These general guidelines constitute guidance to the Investigator and may be supplemented by discussions with the Medical Monitor representing the Sponsor. The guidance applies to all immuno-oncology agents and regimens.

A general principle is that differential diagnoses should be diligently evaluated according to standard medical practice. Non-inflammatory etiologies should be considered and appropriately treated.

[figure not shown]
Corticosteroids are a primary therapy for immuno-oncology drug-related adverse events. The oral equivalent of the recommended IV doses may be considered for ambulatory patients with low-grade toxicity. The lower bioavailability of oral corticosteroids should be taken into account when switching to the equivalent dose of oral corticosteroids.

Consultation with a medical or surgical specialist, especially prior to an invasive diagnostic or therapeutic procedure, is recommended.

The frequency and severity of the related adverse events covered by these algorithms will depend on the immuno-oncology agent or regimen being used.

GI Adverse Event Management Algorithm

Rule out non-inflammatory causes. If non-inflammatory cause is identified, treat accordingly and continue I-O therapy.
Opiates/narcotics may mask symptoms of perforation. Infliximab should not be used in cases of perforation or sepsis.

[figure not shown]
Patients on IV steroids may be switched to an equivalent dose of oral corticosteroids (eg, prednisone) at start of tapering or earlier, after sustained clinical improvement is observed. Lower bioavailability of oral corticosteroids should be taken into account when switching to the equivalent dose of oral corticosteroids.

* Discontinue for Grade 4 diarrhea or colitis. For Grade 3 diarrhea or colitis, 1) Nivolumab monotherapy: Nivolumab can be delayed. 2) Nivolumab+ Ipilimumab combination: Ipilimumab should be discontinued while nivolumab can be delayed. Nivolumab monotherapy can be resumed when symptoms improve to Grade 1. Please refer to protocol for dose delay and discontinue criteria for other combinations.

28-Sep-2020

Renal Adverse Event Management Algorithm

Rule out non-inflammatory causes. If non-inflammatory cause, treat accordingly and continue I-O therapy.

[figure not shown]
Patients on IV steroids may be switched to an equivalent dose of oral corticosteroids (eg, prednisone) at start of tapering or earlier, after sustained clinical improvement is observed. Lower bioavailability of oral corticosteroids should be taken into account when switching to the equivalent dose of oral corticosteroids.

28-Sep-2020

Pulmonary Adverse Event Management Algorithm

Rule out non-inflammatory causes. If non-inflammatory cause, treat accordingly and continue I-O therapy.

Evaluate with imaging and pulmonary consultation.

[figure not shown]

Patients on IV steroids may be switched to an equivalent dose of oral corticosteroids (eg, prednisone) at start of tapering or earlier, after sustained clinical improvement is observed. Lower bioavailability of oral corticosteroids should be taken into account when switching to the equivalent dose of oral corticosteroids.

28-Sep-2020

Hepatic Adverse Event Management Algorithm

Rule out non-inflammatory causes. If non-inflammatory cause, treat accordingly and continue I-O therapy.
Consider imaging for obstruction.

Patients on IV steroids may be switched to an equivalent dose of oral corticosteroids (e.g. prednisone) at start of tapering or earlier, after sustained clinical improvement is observed. Lower bioavailability of oral corticosteroids should be taken into account when switching to the equivalent dose of oral corticosteroids.

[figure not shown]
[^] Please refer to protocol dose delay and discontinue criteria for specific details.

*The recommended starting dose for AST or ALT > 20 x ULN or bilirubin >10 x ULN is 2 mg/kg/day methylprednisolone IV.

28-Sep-2020

Endocrinopathy Adverse Event Management Algorithm

Rule out non-inflammatory causes. If non-inflammatory cause, treat accordingly and continue I-O therapy.
Consider visual field testing, endocrinology consultation, and imaging.

[figure not shown]

Patients on IV steroids may be switched to an equivalent dose of oral corticosteroids (eg, prednisone) at start of tapering or earlier, after sustained clinical improvement is observed. Lower bioavailability of oral corticosteroids should be taken into account when switching to the equivalent dose of oral corticosteroids.

28-Sep-2020

Skin Adverse Event Management Algorithm

Rule out non-inflammatory causes. If non-inflammatory cause, treat accordingly and continue I-O therapy.

Patients on IV steroids may be switched to an equivalent dose of oral corticosteroids (e.g. prednisone) at start of tapering or earlier, after sustained clinical improvement is observed. Lower bioavailability of oral corticosteroids should be taken into account when switching to the equivalent dose of oral corticosteroids.

[figure not shown]
*Refer to NCI CTCAE v5 for term-specific grading criteria.

[^]If Steven-Johnson Syndrome (SJS), toxic epidermal necrosis (TEN), Drug Reaction with Eosinophilia and Systemic Symptoms (DRESS) is suspected, withhold I-O therapy and refer patient for specialized care for assessment and treatment. If SJS, TEN, or DRESS is diagnosed, permanently discontinue I-O therapy.

28-Sep-2020

Neurological Adverse Event Management Algorithm

Rule out non-inflammatory causes. If non-inflammatory cause, treat accordingly and continue I-O therapy.

[figure not shown]
Patients on IV steroids may be switched to an equivalent dose of oral corticosteroids (eg. prednisone) at start of tapering or earlier, after sustained clinical improvement is observed. Lower bioavailability of oral corticosteroids should be taken into account when switching to the equivalent dose of oral corticosteroids.

[^]Discontinue for any grade myasthenia gravis, Guillain-Barre syndrome, treatment-related myelitis, or encephalitis.

28-Sep-2020

Myocarditis Adverse Event Management Algorithm

Rule out non-inflammatory causes. If non-inflammatory cause, treat accordingly and continue I-O therapy.

Patients on IV steroids may be switched to an equivalent dose of oral corticosteroids (eg, prednisone) at start of tapering or earlier, after sustained clinical improvement is observed. Lower bioavailability of oral corticosteroids should be taken into account when switching to the equivalent dose of oral corticosteroids.
Prophylactic antibiotics should be considered in the setting of ongoing immunosuppression.

28-Sep-2020

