Table 7.4-1: Adverse Event Criteria for Delay, Resume, and Discontinuation of Nivolumab

Drug-related AE per NCI CTCAE v5	Severity	Action Taken	Clarifications, Exceptions, and Resume Criteria
Encephalitis	Any Grade encephalitis	Delay dose	After workup for differential diagnosis (ie, infection, tumor related), if encephalitis is not drug related, then dosing may resume when AE resolves
	Any Grade drug-related encephalitis	Permanently discontinue	
Myelitis	Any Grade myelitis	Delay dose	After workup for differential diagnosis (ie, infection, tumor related), if myelitis is not drug related, then dosing may resume when AE resolves
	Any Grade drug-related myelitis	Permanently discontinue	
Neurological (other than GBS, MG, encephalitis, or myelitis)	Grade 2	Delay dose	Dosing may resume when AE resolves to baseline
	Grade 3 or 4	Permanently discontinue	
Myocarditis			
Myocarditis	Symptoms induced from mild to moderate activity or exertion	Delay dose	Dosing may resume after myocarditis has resolved
	Severe or life-threatening, with symptoms at rest or with minimal activity or exertion and/or where intervention indicated	Permanently discontinue	
Other Clinical AEs			
Pancreatitis: Amylase or Lipase Increased	Grade 3 with symptoms	Delay dose	Note: Grade 3 increased amylase or lipase without signs or symptoms of pancreatitis does not require dose delay Dosing may resume when participant becomes asymptomatic
	Grade 4	Permanently discontinue	

Table 7.4-1: Adverse Event Criteria for Delay, Resume, and Discontinuation of Nivolumab

Drug-related AE per NCI CTCAE v5	Severity	Action Taken	Clarifications, Exceptions, and Resume Criteria
Uveitis	Grade 2 uveitis	Delay dose	Dosing may resume if uveitis responds to topical therapy (eye drops) and after uveitis resolves to Grade \leq 1 or baseline. If participant requires oral steroids for uveitis, then permanently discontinue study drug
	Grade 3 or 4 uveitis	Permanently discontinue	
Other Drug-related AE (not listed above)	Grade 2 non-skin AE, except fatigue	Delay dose	Dosing may resume when AE resolves to Grade \leq 1 or baseline value
	Grade 3 AE - First occurrence lasting \leq 7 days	Delay dose	Dosing may resume when AE resolves to Grade \leq 1 or baseline value
	Grade 3 AE - First occurrence lasting $>$ 7 days	Permanently discontinue	
	Recurrence of Grade 3 AE of any duration	Permanently discontinue	
	Grade 4 or life-threatening adverse reaction	Permanently discontinue	
Other Laboratory Abnormalities			

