8.1.2 Discontinuation of BCG

BCG treatment should be permanently discontinued for the following:

- Any event requiring discontinuation of nivolumab/nivolumab-placebo as in [Section 8.1.1](#)
- Any AE, laboratory abnormality, or intercurrent illness which, in the judgment of the investigator, presents a substantial clinical risk to the participant with continued BCG dosing
- Systemic BCG reaction (see current BCG prescribing information for description)
- BCG infection (see current BCG prescribing information for description)

Participant may continue nivolumab/nivolumab-placebo treatment if BCG is discontinued.

The duration of treatment with BCG is based on global standard evidence-based guidelines ([Section 5.4.5](#)). Every effort should be made to treat participants with the full course of BCG as defined in the protocol, although if the participant and investigator agree that it is in the participant's best interests to discontinue BCG treatment, the participant should be counselled appropriately and the reason for discontinuation should be documented in the CRF.

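### For encephalitis or myelitis caused by infection or tumor, the Appendix 5 neurological algorithm says to continue treatment while Table 7.4-1 says to delay until the event resolves, and the algorithm's footnote on encephalitis is ambiguous

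*Combined protocol and SAP*

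**What the plan says.** Table 7.4-1 in Section 7.4 gives encephalitis two rows. The first delays the dose at any grade and adds: "After workup for differential diagnosis (ie, infection, tumor related), if encephalitis is not drug related, then dosing may resume when AE resolves". The second, headed "Any Grade drug-related encephalitis", requires permanent discontinuation. Myelitis has the same pair of rows, the second headed "Any Grade drug-related myelitis".

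The neurological algorithm in Appendix 5 opens with: "Rule out non-inflammatory causes. If non-inflammatory cause, treat accordingly and continue I-O therapy". Its footnote reads: "Discontinue for any grade myasthenia gravis, Guillain-Barre syndrome, treatment-related myelitis, or encephalitis".

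Four other places bear on how these texts fit together:

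- Section 9.2, in defining immune-mediated events, gives infection and tumor progression as examples of non-inflammatory causes.
- Sections 7.4.3.1, 7.4.4.1 and 8.1.1 tie delay, resumption and permanent discontinuation of nivolumab or placebo to Table 7.4-1.
- Section 7.4.5 refers investigators to the Appendix 5 algorithms for several groups of events, neurological events among them.
- The introduction to Appendix 5 describes its content as general guidance, applicable to every immuno-oncology agent and regimen, and speaks of the events covered as related adverse events.

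**The concern.** A site facing encephalitis or myelitis has two places to look, and the protocol points it to both. If the cause proves to be infection or tumor, the algorithm header says treatment goes on, while the table says it waits for resolution. A site that reads only the footnote could also conclude that encephalitis ends treatment whatever its cause.

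At stake is whether a participant with a serious neurological event is dosed or held. Enrollment has closed, but participants on treatment may continue, so the rules are still live. Section 10.3.2 also still tabulates adverse events leading to discontinuation by treatment group. Sites that read the footnote differently would feed that table differently.

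**Working it through.** No arithmetic applies, and the plan states no figure on this point. The check sets the texts side by side for encephalitis or myelitis that is traced to infection or tumor and has not yet resolved.

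| Text | Trigger | Instruction |
|---|---|---|
| Table 7.4-1, any-grade rows | Event of any grade, found on work-up not to be drug related | Delay; dosing may resume when the event resolves |
| Appendix 5, neurological header | Non-inflammatory cause | Treat the cause and continue immunotherapy |
| Appendix 5, neurological footnote | Treatment-related myelitis; encephalitis with or without that limit | Discontinue |

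**Header against table.** The triggers are worded differently: one turns on non-inflammatory cause, the other on lack of drug relation. They overlap for infection and tumor, because the table names these as the work-up alternatives and Section 9.2 lists infection and tumor progression as non-inflammatory. In that overlap the header says "If non-inflammatory cause, treat accordingly and continue I-O therapy", and the table makes resumption wait for resolution. The table's first column is headed as drug-related events, but these rows state expressly what happens when the event is not drug related, so the case falls within the table. The two instructions differ, and this does not depend on how the footnote is read.

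**Footnote against table.** There are two readings.

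- The treatment-related limit covers both myelitis and encephalitis. The footnote then agrees with the two drug-related rows of the table and does not reach the event considered here.
- The limit covers myelitis only, which the comma before the last item allows. The footnote then discontinues encephalitis of any cause, against the table's statement that "if encephalitis is not drug related, then dosing may resume when AE resolves".

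The wording does not decide between them.

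**Footnote against header.** There is no clear conflict. The header sets non-inflammatory causes aside first, and the footnote sits inside an algorithm for related events.

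**Precedence.** Table 7.4-1 is the mandatory text through Sections 7.4.3.1 and 8.1.1. The protocol does not say that it prevails over Appendix 5. The hepatic algorithm refers readers back to the protocol's delay and discontinuation criteria; the visible text of the neurological algorithm does not. Section 3.1.1 says that Amendment 01 overrides existing requirements, but this does not help: the summary of changes shows that the same amendment added the table and replaced the algorithms.

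**The case against.** The strongest reply is that the mandatory text gives a single rule. Table 7.4-1 governs delay, resumption and discontinuation, Appendix 5 is guidance, and its header is a generic sentence repeated across the algorithms. Nor does that sentence exclude a hold: in the skin algorithm it stands beside an instruction to withhold treatment while a severe skin reaction is only suspected. Section 7.4.3.1 also lets the investigator delay for any event judged to warrant it.

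Much of this stands. It limits the practical effect, and it shows that the header can coexist with a hold during work-up. It does not cover the time after the cause has been identified as infection or tumor and before the event has resolved. In that interval the header says continue and the table says wait. A site sent to Appendix 5 by Section 7.4.5 is not told to prefer the table.

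A reader might infer more: that the protocol gives three dispositions for encephalitis that is not drug related, with the footnote supplying a stop. The documents do not establish that. The stop needs one reading of an ambiguous modifier, and the other reading agrees both with the table and with the related-event scope of Appendix 5. The algorithm chart is not reproduced in the available text, so the place where the footnote mark attaches cannot be checked.

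A reader might also infer that such a stop would end BCG, because Section 8.1.2 lists "Any event requiring discontinuation of nivolumab/nivolumab-placebo as in" Section 8.1.1. But Section 8.1.1 rests on Table 7.4-1, investigator-judged risk and prolonged delay. It does not rest on the Appendix 5 footnote, so loss of BCG does not follow from the footnote alone.

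**Conclusion.** The point holds as an internal inconsistency. One conflict is firm: continue against delay until resolution, for encephalitis or myelitis due to infection or tumor. One ambiguity comes with it: whether the treatment-related limit in the footnote covers encephalitis.

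The conclusion rests on Section 9.2's examples of non-inflammatory causes carrying over to the algorithm header. It is confined to the overlap between non-inflammatory and not drug related. An inflammatory cause unrelated to the drug would not meet the header at all.

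The practical size is small. The protocol gives no rate for either event, and Section 3.1.1 puts enrollment below 5% of target when the study closed; if the target is the 700 participants to be randomized, that is fewer than 0.05 × 700 = 35. No arm sizes are given, so a percentage-point effect on the by-arm discontinuation table cannot be derived. The safety output is descriptive, and no inference depends on it. The reason to act is that conflicting instructions on re-dosing after a serious neurological event can be removed cheaply.

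**What to change.** Reconcile the three texts:

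- Bring the neurological algorithm header and the any-grade encephalitis and myelitis rows of Table 7.4-1 into agreement, or state in Section 7.4.5 or Appendix 5 which text governs when they differ.
- State in the footnote whether the treatment-related limit applies to encephalitis as well as myelitis.

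The clinical team decides the rule; the statistical request is only that the places match. The cost is a wording change to one footnote and one header sentence, or one added sentence on precedence. It needs no new data collection and no change to the analysis.
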